Note: For 're-treatment' patients who go onto have a subsequent 12 months of treatment the same assessments should be done as in the screening and the first 12 month treatment period with the exception of the PK, ADA, sPD-L1, PGx and biopsy assessments which do not need to be collected a second time.

Table 2 Schedule of study procedures: follow-up for patients who have completed MEDI4736 treatment and achieved disease control (until confirmed progression of disease) and patients who have discontinued MEDI4736 due to toxicity in the absence of confirmed progression of disease

Evaluation	Time Since Last Dose of MEDI4736							
	Day (± 3)	Months (± 1 week)						12 Months and Every 6 Months (± 2 weeks)
	30	2	3	4	6	8	10	
Physical examination	X							
Vital signs (temperature, respiratory rate, blood pressure, pulse, oxygen saturation; see Section 6.4.8)	X							
Weight	X							
Electrocardiogram	X							
AE/SAE assessment	X	X	X					
Concomitant medications	X							
Palliative radiotherapy	As clinically indicated (see Section 5.1) →							
World Health Organisation performance status	X		X					
Subsequent anti-cancer therapy	X	X	X	X	X	X	X	X
Survival status: phone contact with patients who refuse to return for evaluations and agree to be contacted		X	X	X	X	X	X	X (every 2 months)
Haematology	X	X	X	X				X
Serum chemistry	X	X	X					
Amylase, lipase (where available)	X	X	X					
Thyroid function tests (TSH, and T3 and T4)	X							
Coagulation parameters ^a	As clinically indicated →							
Urinalysis	As clinically indicated →							
Pharmacokinetic assessment			X					

Table 2 Schedule of study procedures: follow-up for patients who have completed MEDI4736 treatment and achieved disease control (until confirmed progression of disease) and patients who have discontinued MEDI4736 due to toxicity in the absence of confirmed progression of disease

Evaluation	Time Since Last Dose of MEDI4736							12 Months and Every 6 Months (±2 weeks)
	Day (±3)	Months (±1 week)						
	30	2	3	4	6	8	10	
Immunogenicity assessment (ADA sampling [including ADA neutralising antibodies] to identify ADA responses in patient circulation)			X					
sPD-L1 concentration (to assess target engagement)			X					
Circulating soluble factors (to assess cytokines, chemokines, growth factors and antibodies against tumour and self antigens in circulation)	X							

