If a patient is withdrawn from the study, see Section 5.9.

Assessments following withdrawal of MEDI4736

Patients who are permanently discontinued from receiving investigational product will remain in the study and will be followed per the study plans in Table 2 or Table 3 including the collection of any protocol-specified blood specimens, unless consent is withdrawn or the patient is lost to follow-up or enrolled in another clinical study. All patients will be followed for survival. Patients who decline to return to the site for evaluations will be offered follow-up by phone as specified in the study plans as an alternative (Table 2 [for follow-up of patients achieving disease control or who are discontinued due to toxicity in the absence of confirmed PD] and Table 3 [for follow-up of patients discontinuing due to confirmed PD]). However, patients who discontinue due to an AE will need to attend all protocol-specified visits and all assessments will be conducted as scheduled.

All patients who have any Grade 3 or 4 laboratory values at the time of discontinuation must have further tests performed and the results recorded on the appropriate eCRF until the laboratory values have returned to Grade 1 or 2, unless these values are not likely to improve because of the underlying disease.

At discontinuation, all on-going study-related toxicities and SAEs must be followed until resolution, unless in the investigator's opinion, the condition is unlikely to resolve due to the patient's underlying disease.

All new AEs occurring for up to 90 days after the last dose of MEDI4736 must be recorded in the eCRF and reported as SAEs, if applicable.

Patients who have disease control following completion of 12 months of treatment or patients who are withdrawn from MEDI4736 treatment for reasons other than confirmed PD will continue to have objective tumour assessments (see [Table 2](#)). Drug or study procedure related SAEs must be captured until the patient completes the follow-up period following discontinuation of study treatment (confirmed PD or permanent withdrawal from the study).

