6.4.3 Recording of adverse events

Time period for collection of adverse events

Adverse events will be collected from time of signature of informed consent, throughout the treatment period and including the follow-up period (90 days after the last dose of investigational product).

SAEs will be recorded from the time of informed consent, throughout the treatment period and including the follow-up period (90 days after the last dose of investigational product).

If a patient discontinues from treatment for reasons other than disease progression, and therefore continues to have tumour assessments using RECIST, drug or procedure-related

SAEs must be captured until the patient is considered to have confirmed PD and will have no further RECIST assessments.

For screening failures (ie, patients who do not receive study treatment), SAEs will be collected from the time of signature of informed consent until the patient is withdrawn from study. Any SAE related to a mandated study procedure should be reported.

Follow-up of unresolved adverse events

During the course of the study all AEs and SAEs should be proactively followed up for each patient. Every effort should be made to obtain a resolution for all events, even if the events continue after discontinuation/study completion.

Any AEs that are unresolved at the patient's last visit in the study are followed up by the investigator for as long as medically indicated, but without further recording in the eCRF. AstraZeneca retains the right to request additional information for any patient with ongoing AE(s)/SAE(s) at the end of the study, if judged necessary.

Post-study events

After the patient has been permanently withdrawn from the study, there is no obligation for the investigator to actively report information on new AE or SAEs occurring in former study patients after the 90-day safety follow-up period. However, if an investigator learns of any SAEs, including death, at any time after the patient has been permanently withdrawn from study, and he/she considers there is a reasonable possibility that the event is related to the investigational product, the investigator should notify AstraZeneca/MedImmune Drug Safety or its representative.

Variables

The following variables will be collected for each AE on the eCRF:

- AE (verbatim)
- The date and time when the AE started and stopped
- The maximum CTCAE grade reported
- CTC grade changes for events of Grade 3 or above
- Whether the AE is serious or not

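### Table 2 schedules AE/SAE assessment only to month 3 after last dose, while Sections 5.8 and 6.4.3 require related SAEs in the same patients to be captured until confirmed progression

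*Protocol*

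**What the plan says.** **Table 2 (Section 3.1).** The table covers two groups. The first is given in its title as "follow-up for patients who have completed MEDI4736 treatment and achieved disease control (until confirmed progression of disease"). The second is those whose treatment ended because of toxicity while progression was not confirmed. The row "AE/SAE assessment" is marked at Day 30, month 2 and month 3 after the last dose. It is blank at months 4, 6, 8 and 10 and in the last column (12 months and every 6 months). The two footnotes concern coagulation tests and imaging; neither extends the row.

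**Section 5.8.** The extended rule opens with the people it covers: "Patients who have disease control following completion of 12 months of treatment or patients who are withdrawn from MEDI4736 treatment for reasons other than" progression that has been confirmed. It refers to Table 2 for their tumour assessments and then states: "Drug or study procedure related SAEs must be captured until the patient completes the follow-up period following discontinuation of study treatment". It gives the end of that period as confirmed progression or permanent withdrawal from the study.

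**Section 6.4.3.** The general window is: "SAEs will be recorded from the time of informed consent, throughout the treatment period and including the follow-up period (90 days after the last dose"). A separate paragraph then extends it for patients who come off treatment without progression and go on with RECIST scans. For events related to the drug or a procedure, it says that "SAEs must be captured until the patient is considered to have confirmed PD and will have no further RECIST assessments".

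**The concern.** Table 2 applies the general 90-day window and leaves out the extension that the text writes for the table's own patients. The table is also the working instruction for sites. Section 5.8 says that patients off treatment are followed according to Table 2 or Table 3, and Section 6.2.2 points to those tables for the follow-up assessments. A site that follows Table 2 exactly is not prompted to carry out a duty that the text states twice as mandatory.

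What is at stake is the completeness of late related SAEs. The patients concerned include those who stopped because of toxicity, and Section 5.5.3.1 singles out immune-mediated events for close monitoring. The trial has a single arm, is intended for a registration package (Section 3.2) and has no data monitoring committee (Section 12.4), so what sites capture carries much of the weight.

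**Working it through.** The plan gives no figure to reproduce. The check compares the schedule with the text and then places the gap on the calendar.

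**Step 1: do the populations match?**

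| Source | Patients covered |
|---|---|
| Table 2 | Completers with disease control; toxicity stoppers without confirmed progression |
| Section 5.8 | Completers with disease control; anyone withdrawn for a reason other than confirmed progression |
| Section 6.4.3 | Patients off treatment for reasons other than progression who continue RECIST assessments |

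Section 5.8 is slightly broader but contains both Table 2 groups.

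**Step 2: do the periods match?**

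| Source | Capture of related SAEs |
|---|---|
| Table 2 row | Scheduled to month 3 |
| Section 5.8 | To confirmed progression or permanent withdrawal |
| Section 6.4.3 | To confirmed progression, with no further RECIST assessments |

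The row agrees with the 90-day window only.

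**Step 3: count the columns.** Table 2 has 8 time columns: Day 30; months 2, 3, 4, 6, 8 and 10; and 12 months onward. AE/SAE assessment is marked in 3 of 8, which leaves 8 − 3 = 5 later columns with none.

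**Step 4: what happens at the later contacts?** Table 2 continues subsequent anti-cancer therapy and survival status, has haematology at month 4 and from 12 months, and continues scans until confirmed progression. None of these carries an AE/SAE entry.

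**Step 5: place the gap on the calendar.** Three months is taken as about 13 weeks.

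- Completer: the last dose is at Week 50 (Section 5.5.2), so month 3 falls at about 50 + 13 = Week 63. Scans every 12 weeks from first infusion then fall at Weeks 72, 84, 96 and so on until confirmed progression, without an AE/SAE enquiry.
- Toxicity stopper, with the last dose at Week 8 assumed for illustration: month 3 falls at about 8 + 13 = Week 21. Scans at Weeks 24, 32, 40, 48, 60 and so on carry no enquiry.

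A completer who restarts treatment returns to Table 1, where AE/SAE assessment is scheduled again, so the gap applies to time off treatment.

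**Step 6: is Table 3 affected?** Its AE/SAE row is the same, but its patients already have confirmed progression. The extended rule does not reach them and the 90-day window is consistent.

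**The case against.** The strongest reply is that the table and the text can both be obeyed. A blank cell does not forbid capture. The duty is explicit in two sections. Section 6.4.2 defines an SAE as arising in any phase, including follow-up, and Section 6.4.4 requires a report within 24 hours of the site becoming aware. Patients are still scanned until confirmed progression, those who stopped for an AE must attend all protocol-specified visits (Section 5.8), and Section 6.4.3 contains an open question about health problems. On this view only a cross-reference is missing.

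Much of this stands. The duty exists, and so do the contacts. A reader might infer from Table 2 that there is no contact after month 3, or that late SAEs are lost altogether; the protocol supports neither. What the reply does not supply is the prompt. Reporting once aware depends on becoming aware, and the open question is not tied to any contact after month 3.

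The reply is also right about the analysis. Section 11.2.1 ends the AE summary tables at 90 days after discontinuation, or earlier if subsequent therapy starts, and its longer-term summaries also end at 90 days. A reader might infer that the planned safety tables are biased, but events after day 90 would not enter them even if captured in full.

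**Conclusion.** The mismatch is real and should be corrected. Table 2 schedules AE/SAE enquiry in 3 of 8 columns, while the text requires capture of related SAEs until confirmed progression in the patients the table covers. The likely effect is under-capture of late related SAEs in safety reporting and the database. The planned AE summary tables and the efficacy endpoints are untouched.

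Two further inferences go beyond the documents. The gap does not concern all patients who stopped for toxicity or all who reached 12 months: Table 2 is limited to those with disease control at completion and those without confirmed progression. Nor can the gap be expressed as a share of required follow-up or a number of missed events. That would need stopping times, progression times and late SAE rates, which the protocol does not give.

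The conclusion assumes that sites work from the schedule, as Sections 5.8 and 6.2.2 direct.

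**What to change.** Reconcile Table 2 with Sections 5.8 and 6.4.3. Since the text states the longer rule twice as mandatory, the direct repair is to continue the AE/SAE row at the existing contacts after month 3 (months 4, 6, 8 and 10, 12 months and later contacts) with a footnote such as:

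*After 90 days from last dose, drug- or study procedure-related SAEs only, until confirmed PD or permanent withdrawal from the study (Sections 5.8 and 6.4.3).*

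Leave Table 3 unchanged. The cost is one table row, one footnote and one extra question at contacts that already take place; no new visit or test is needed.

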3.2 Rationale for study design, doses and control groups

Current therapies for advanced NSCLC have poor outcomes and there is still a significant unmet medical need for additional treatment options for use in this patient population. Patients who fail second-line chemotherapy usually have a poor prognosis with median survival of <6 months. The outlook for refractory advanced NSCLC is extremely poor, with response to further systemic therapy of <10% ([Hanna et al 2004](#)).

Single agent chemotherapy is an acceptable option for patients who fail first- or second-line systemic treatment. However, the impact on PFS and OS is generally modest; thus, novel and more effective therapeutic strategies are needed. Erlotinib (TARCEVA[®]), an EGFR inhibitor, also provides a modest improvement in OS in patients who have failed first- or second-line chemotherapy ([TARCEVA[®] prescribing information](#)). In a randomised, placebo-controlled, double-blind trial comparing erlotinib with placebo, patients treated with erlotinib showed OS of 6.7 months versus 4.7 months for placebo (hazard ratio: 0.73; 95% confidence interval [CI]: 0.61 to 0.86); PFS was 2.3 months for the erlotinib group versus 1.8 months for the placebo group (hazard ratio: 0.59; 95% CI: 0.50 to 0.70).

The single-arm study design will enable rapid recruitment and the study will be used as part of the registration package for MEDI4736 aimed at a patient population with significant clinical unmet need.

Although clinical experience with MEDI4736 is limited, currently available data from the MEDI4736 FTIH study (Section 1.1.3.2 and MEDI4736 IB), indicates encouraging response rates and DoR, with a manageable safety profile in patients with a variety of solid malignancies, including patients with advanced NSCLC who have failed multiple lines of therapy.

Based on an analysis of the dose-escalation data from the ongoing FTIH study, a dose of 10 mg/kg Q2W administered for up to a maximum of 12 months is recommended for further development. This dosing regimen is expected to have a high probability of ensuring a response in the majority of patients.

This recommendation is supported by multiple lines of evidence including: in-vitro data, nonclinical activity, clinical PK-pharmacodynamics, clinical biomarkers, and clinical activity data collected from the FTIH study. Based on the FTIH data, MEDI4736 exhibited non-linear (dose-dependent) PK consistent with target mediated drug disposition. A dose-dependent decrease in peripheral soluble PD-L1 was observed over the dose range of 0.1 to 10 mg/kg Q2W; consistent with engagement of MEDI4736 with PD-L1. Significant soluble PD-L1 (>90%) suppression at trough was observed with doses ≥ 0.3 mg/kg Q2W. Pharmacokinetic parameters such as dose-normalised area under the plasma drug concentration-time curve and $t_{1/2}$ increased over the dose range of 0.1 to 10 mg/kg Q2W and approached linearity at 3 mg/kg Q2W; suggesting near complete target saturation (membrane bound and soluble PD-L1) with 3 mg/kg Q2W. The expected mean trough concentration following 3 mg/kg Q2W MEDI4736 is ~ 50 $\mu\text{g/mL}$. Although clinical activity has been observed at lower doses, and DLTs have not been observed at the highest dose studied (10 mg/kg Q2W), this dose/schedule is

anticipated to maintain levels above a target median trough concentration (100 µg/mL). The target trough serum concentration of 100 µg/mL accounts for the variability in PK (~50%), pharmacodynamic response and clinical activity (up to 100%) anticipated in a diverse cancer patient population and to maintain sufficient PK exposure in case of an ADA impact. The target serum concentration of 100 µg/mL can be maintained with the 10 mg/kg Q2W dosing regimen. Data generated during the dose escalation phase of the FTIH study also suggest that higher doses (ie, 10 mg/kg Q2W) may be associated with better clinical activity while still providing an acceptable safety profile. Dose-related changes in a variety of peripheral biomarkers have been observed over the dose range of 0.1 to 3 mg/kg Q2W. Thus far, a low level of immunogenicity has been observed. Of the 220 patients who received MEDI4736 monotherapy and for whom PK/ADA data were available as of July 2014, 5 were detected to be ADA positive, with an impact on PK/pharmacodynamics reported in 1 patient. Thus, the clinical activity observed coupled with the safety profile, translational science correlates, and non-clinical data supports further development with a dose of 10 mg/kg Q2W.

The patient population in this single arm study will be split into 3 cohorts based on patients' *EGFR* TK mutation and *ALK* fusion status and also tumour PD-L1 expression. The primary rationale for this is that there are clear biological and treatment outcome differences between patients with NSCLC with *EGFR/ALK* positive tumours and those patients with *EGFR/ALK* wild type/unknown tumour status. It is considered that patients with "actionable mutations", which have subsequently received the appropriate molecularly targeted therapy (ie, EGFR or ALK TKI) as part of their prior courses of treatment, comprise a subgroup of NSCLC patients with a different clinical course and prognosis distinct from those with proven *EGFR/ALK* wild type status. Therefore, assessing efficacy and safety separately in patients with mutant or *EGFR/ALK* wild type/unknown tumours is a reasonable choice based on the natural history of the disease and response to therapy, which ultimately impacts prognosis and OS. This rationale also supports the inclusion of eligible patients with unknown *EGFR* TK mutation or *ALK* fusion status in the *EGFR/ALK* wild type cohort; in the event that no valid test result is available. Collection of appropriate tissue samples to enable retrospective confirmation/classification of patients according to their *EGFR* mutation or *ALK* fusion status will ensure greater confidence in our ability to understand MEDI4736 activity in each patient type.

Published experience with the anti-PD-1/PD-L1 class suggests that it might be beneficial to enrich the patient population by selecting those patients who are considered to be most likely to respond to therapy. To date, no assay has been established/validated and no single approach has proven accurate for patient enrichment for immune-mediated therapies. However, independent data from multiple sources using different assays and scoring methods suggests that PD-L1 expression on tumour cells and/or tumour-infiltrating cells may be associated with greater clinical benefit. For example, data presented by Roche at the Annual Meeting of the American Society of Clinical Oncology 2013 (Powderly et al 2013) suggested that PD-L1 expression on infiltrating lymphocytes in NSCLC, melanoma, and renal cell carcinoma patient cohorts is associated with greater clinical benefit from anti-PD-L1 treatment. Using a proprietary assay for PD-L1 IHC, they found a 36% ORR in patients who had PD-L1 positive tumours with 50% of patients with PD-L1 positive tumours having SD

and 33% having PRs. In contrast, in patients with PD-L1 negative tumours, they found only a 13% ORR with 28% of patients having SD and 13% having PRs. Similarly, in data presented at the Annual Meeting of the American Society of Clinical Oncology 2013 by Bristol-Myers Squibb ([Grosso et al 2013](#)), PD-L1 staining when assessed using a different method and scoring algorithm appeared to be associated with greater clinical benefit in patients with metastatic melanoma treated with nivolumab (anti-PD-1). They found a 44% ORR in patients with PD-L1 positive tumours versus a 17% ORR in patients with PD-L1 negative tumours. Additionally, in their studies, patients with tumours that were PD-L1 positive had a higher PFS (9.1 versus 2.0 months) and OS than patients with PD-L1 negative tumours (21 versus 12 months). Also, in a data set presented by Merck & Co at the World Conference on Lung Cancer ([Garon et al 2013](#)), analysis of the relationship between PD-L1 expression status and response rates in a cohort of patients with NSCLC indicated that tumour samples displaying high levels of expression (according to their assay criteria) were associated with response rates of 67% (6/9) per irRC and 57% (4/7) per RECIST. In contrast, tumour samples expressing zero/low levels of PD-L1 were associated with response rates of 4% (1/24) per irRC and 9% (2/22) per RECIST.

Efficacy data on the NSCLC patients in Study 1108, presented at ESMO 2014 (cut-off date of 21 August 2014), showed a disease control rate at 12 weeks of 41% and ORR of 16% among 162 evaluable patients, with activity observed in both squamous and non-squamous histologies. The ORR was higher in patients with PD-L1 positive tumours (25%; 12 CR/PR; n=48) compared to patients with PD-L1 negative tumours (10%; 7 CR/PR; n=74) ([Antonia et al 2014](#)).

AstraZeneca data on file indicate that the best predictor of response using the PD-L1 assay is tumour membrane expression and that the current cut-off of 25% tumour cell staining effectively enriches for responders in the PD-L1-positive group. A subpopulation of patients within the positive group possessed tumour tissue samples characterised by $\geq 90\%$ of tumour cells scoring membrane-positive for PD-L1. This group appeared to have a high likelihood of response (ORR $\sim 39\%$; 7 CR/PR; n=18). Therefore the potential benefit of enriching the patient population further by identifying patients whose NSCLC tumours are PD-L1 positive at or above the 90% threshold will be assessed in Cohort 3 of this study.

Given that tumours evolve with time and in response to treatment, archived samples of tumour tissue may not accurately reflect the current state of disease due to the time intervals that may occur between diagnostic sample collection and late-line treatment. Therefore, archived samples will be collected as well as a recent (≤ 3 months) tumour biopsy (taken following completion of the most recent therapy) to ascertain the PD-L1 status and to gain understanding about the relationship between these samples in determining which sample type may have the greatest utility for informing us about patients.

The primary aim of this study is to determine the efficacy of MEDI4736 (10 mg/kg Q2W via iv infusion) in terms of ORR. ORR can be a useful endpoint in single arm studies because it is a direct measure of the drug's anti-tumour activity (Pazdur 2008). The use of ORR in the third/fourth-line setting, especially when the responses are sustained and durable (a key

feature of immunotherapy), is justified because it is anticipated that it will serve as an early measure of clinical benefit that may be confirmed by the survival endpoint employed in a planned randomised confirmatory study. The kinetics of anti-PD-L1 response also favour the use of ORR as a potential surrogate endpoint because response occurs from the first 6 weeks of treatment (earlier than other immunotherapeutic agents such as anti-CTLA-4) ([Brahmer et al 2012](#), [Spigel et al 2013](#)). In patients treated with immunotherapies, including MEDI4736, relapse after response can be uncommon; reinforcing the importance of ORR as a likely surrogate for clinical benefit.

Anti-tumour activity will be assessed according to RECIST v1.1 guidelines. The primary analysis will be based on the programmatically-derived ORR based on ICR assessments using RECIST, and using all scans regardless of whether they were scheduled or not. Sensitivity analyses of ORR from the site investigator tumour data will also be performed according to RECIST 1.1 and additionally from the ICR according to RECIST, modified for confirmation of progression and irRECIST 1.1 (see Section 11.2).

This is because the response to immunotherapy may differ from typical responses observed with cytotoxic chemotherapy including the following (per [Wolchok et al 2009](#)):

1. Response to immunotherapy may be delayed
2. Response to immunotherapy may occur after PD by conventional criteria
3. The appearance of new lesions may not represent PD with immunotherapy
4. SD while on immunotherapy may be durable and represent clinical benefit.

Based on the above-described unique response to immunotherapy and based on guidelines from regulatory agencies, eg, European Medicines Agency's "Guideline on the evaluation of anti-cancer medicinal products in man" ([EMA/CHMP/205/95/Rev.4](#)) for immune modulating anti-cancer compounds, the study implements the following:

- RECIST will be modified so that PD must be confirmed at the next scheduled visit, preferably, and no earlier than 4 weeks after the initial assessment of PD in the absence of clinically significant deterioration. Treatment with MEDI4736 will continue between the initial assessment of progression and confirmation for progression.
- In addition, patients may continue to receive MEDI4736 beyond confirmed PD in the absence of clinically significant deterioration and if investigators consider that patients continue to receive benefit from treatment.

Modification of RECIST as described may discourage the early discontinuation of MEDI4736 and provide a more complete evaluation of its anti-tumour activity than would be seen with conventional response criteria. Nonetheless, the primary analysis of each efficacy endpoint will be conducted based on RECIST 1.1 criteria.

Of note, clinically significant deterioration is considered to be a rapid tumour progression that necessitates treatment with anti-cancer therapy other than MEDI4736 or with symptomatic progression that requires urgent medical intervention (eg, central nervous system metastasis, respiratory failure due to tumour compression, spinal cord compression).

Justification for re-treatment beyond 12 months of MEDI4736:

- Targeted therapies have significantly increased both the rate and durability of response in patients with biomarker-enriched subsets of cancers including advanced NSCLC (eg, gefitinib and erlotinib in EGFR mutation positive, and crizotinib in ALK translocation positive) as well as in metastatic or unresectable melanoma (vemurafenib and dabrafenib in BRAF V600E mutation, trametinib in both V600E and V600K) (Maemondo et al 2010, Mok et al 2009, Mitsudomi et al 2010, Rosell et al 2011, Shaw et al 2013). Nevertheless, responses are mostly partial, and relapses are inevitable once resistance mechanisms emerge. Furthermore, the potential for tumour “addiction” and rapid clinical deterioration at the time of withdrawal and/or progression has been described (Asami et al 2013, Yoshimura et al 2013, Kim et al 2011, Yang et al 2013, Rizos et al 2014).
- In contrast to targeted therapy, responses have been observed upon retreatment with immune-mediated therapy. Responses with immune-mediated therapy are no different than responses to initial treatment in terms of time to response, DoR, or maintenance of response beyond treatment discontinuation (Hodi et al 2010, Forde et al 2014).

Therefore, patients who achieve and maintain disease control (ie, complete response [CR], PR or SD) through to the end of the 12-month MEDI4736 treatment period may also restart treatment with MEDI4736 upon evidence of disease progression during follow-up (maximum of 12 months of further treatment).

The patient must **not have** received an intervening systemic anti-cancer therapy after discontinuing MEDI4736 and should have a baseline tumour assessment within 28 days of restarting treatment with MEDI4736 (see [Table 1](#)).

Biological samples will be used to explore potential biomarkers in tumour, plasma and/or serum, which may influence the progression of cancer (and associated clinical characteristics) and/or response.

Blood samples will be taken to allow for future exploratory research into genes/genetic factors that may influence response of MEDI4736 and/or agents used in combination and/or as comparators (PGx optional [DNA element]).

